2.4 Risk/Benefit Assessment

2.4.1 Viltolarsen

There were no important identified risks of viltolarsen in the current clinical development program. [REDACTED]

[REDACTED] No serious adverse reactions were recognized in the reporting period of the current Drug Safety Update Report (14 May 2019 to 13 May 2020), and there were no actions taken for safety reasons, or any significant changes in the IB.

At present, none of the safety risks identified during the current reporting period were considered to be important risks. Further, nonclinical adverse effects previously identified as important potential risks have not been observed in any of the human studies conducted to date.

2.4.2 Procedures

Risks due to study-related procedures are detailed below.

Blood sample collection for hematology, chemistry, and PK is associated with the usual risks of a blood draw which include pain, bruising at the point where the blood is taken, redness and swelling of the vein, infection, and a rare risk of fainting. In order to decrease any of these possible risks the sites will employ pediatric trained staff and will use a numbing cream, if desired by the patient, to reduce the risk of pain.

Function and strength tests will be performed during this study. These include the Brooke and Vignos scales, Performance of Upper Limb (PUL), North Star Ambulatory Assessment (NSAA), and hand-held dynamometer. All tests are associated with muscle soreness, fatigue, and falls.

Quantitative muscle strength by hand-held dynamometer may cause fatigue and muscle soreness.

While wearing the ActiGraph GT9x on the wrist, there is a small risk for discomfort or redness at the wear site. Padding will be provided and patients will be instructed to remove the ActiGraph if they experience any discomfort (i.e., redness, irritation, pressure points) and contact the investigator immediately.

3 STUDY OBJECTIVES AND ENDPOINTS

Primary Objective	Primary Endpoints

 To evaluate the safety and tolerability of viltolarsen administered IV at weekly doses of 80 mg/kg in ambulant and non-ambulant boys ≥ 8 years of age with DMD 	
 Vital signs Physical examination Renal ultrasound Echocardiogram Clinical laboratory tests 
 Hematology and clinical chemistry Urinalysis Urine cytology 12-lead electrocardiogram (ECG) Anti-viltolarsen antibodies Anti-dystrophin antibodies TEAEs and SAEs
Secondary Objective	Secondary Endpoints

 To compare the efficacy of viltolarsen administered IV at weekly doses of 80 mg/kg over a 48-week Treatment Period versus natural history controls in ambulant and non-ambulant boys ≥ 8 years of age with DMD 	
 Peak Expiratory Flow (PEF) Forced Vital Capacity (FVC) Forced expiratory volume in 1 second (FEV1) PUL Brooke scale Vignos scale Hand-held dynamometer NSAA
Exploratory Objectives	Exploratory Endpoints

 To evaluate health-related quality of life impact of viltolarsen treatment on patient's DMD 	
 Treatment Satisfaction Questionnaire (TSQM) Pediatric Outcome Data Collection Instrument (PODCI) Personal Adjustment and Role Skills Scale, 3rd edition (PARS III) Questionnaire

 To evaluate strength of cough in patients with DMD 	
 Peak Cough Flow (PCF)

 To evaluate preservation of ambulation of patients with DMD 	
 Loss of ambulation

 To evaluate daily activity and sleep-wake patterns to explore impact of viltolarsen treatment on patient's DMD 	
 Accelerometry measures of activity and sleep-wake patterns

4 HYPOTHESIS

Viltolarsen administered at 80 mg/kg/week is safe and well tolerated and ameliorates the clinical course of ambulant and non-ambulant boys with DMD as assessed by a muscle functional measure. The improvement in function is due to an increase in muscle tissue dystrophin expression.

5 INVESTIGATIONAL PLAN

5.1 Overall Study Design and Plan

This is a Phase 2, open-label study with DMD boys receiving 80 mg/kg viltolarsen administered IV at weekly doses in ambulant and non-ambulant boys ≥ 8 years of age with DMD over a 48-week Treatment Period. See [Section 1.1](#) for study schema.

5.1.1 Number of Centers

The study will be conducted at approximately 10 study sites in approximately 6 countries, including China, Italy, Russia, Spain, Turkey, and the US.

5.2 Design Implementation

5.2.1 Randomization

Not applicable.

5.2.2 Investigational Product Dosing

The dose per patient (in milligrams) will be calculated based on body weight in kilograms, collected per the protocol. Details of dose preparation can be found in the study Investigational Product Information Manual (IPIM). Doses will be administered by an IV infusion over a 1-hour period. All missed or incomplete doses will be documented. The dispensed investigational product (IP) vials will be stored at the research site until drug accountability is verified by the pharmacy monitor.

In the event it becomes necessary, or at the discretion of the parent/guardian, in consultation with the investigator and consulting surgeon and following adequately informed and voluntary patient/guardian consent and child assent, a totally implantable central venous access device (TICVAD) may be used, contingent upon approval by local and/or country-specific regulatory body(ies). Implantable central venous access (CVA) ports will be considered on a case-by-case basis for patients who experience difficulty with peripheral venous access. Discussions regarding implantable ports for patients will include the study site investigator, medical monitor, and sponsor. Before final decision, NS Pharma, Inc. will obtain documentation from the investigator that the consulting surgeon who will place the port holds hospital privileges as a board eligible/board certified surgeon. Implantation should not proceed without sponsor

approval. Care of the TICVAD (including aseptic access and flushing) and patient monitoring must be performed by qualified personnel according to the site's standard operating procedure.

An alternative method of CVA may only be considered in the case of a documented contraindication to the placement of a TICVAD.

5.2.3 Potential Design Modifications Due to Toxicities

Dose reductions may be necessary for individual patients. The dose level will be determined jointly by the investigator, study chair, and medical monitor in consultation with the sponsor.

5.2.4 Dose Interruptions

Infusion interruptions may be necessary for individual patients. Infusion interruptions should be handled in accordance with standard procedures should an acute reaction occur during an infusion. Sites should notify the medical monitor in the event of an infusion interruption due to an acute reaction.

5.3 Study Duration and Dates

The expected study duration for each patient is approximately 56 weeks. The Pretreatment Phase will last approximately 28 days (inclusive of Screening Visit and Pretreatment Visit). The Treatment Phase will last approximately 48 weeks. The follow-up phase is 30 days.

5.3.1 End of Study Definition

Primary Completion: The primary completion date is the same as the end of study date and is the date when the last patient has completed the study (i.e., last patient last visit).

If the study concludes prior to the primary completion date originally planned in the protocol (i.e., early termination of the study), then the primary completion date will be the date when the last patient is assessed or receives an intervention for evaluation in the study (i.e., last patient last visit).

End of Study: The end of study date is defined as the date when the last patient at the site is assessed or receives an intervention for evaluation in the study (i.e., last patient last visit).

5.3.2 End of Treatment

End of treatment is defined as the last assessment for the protocol-specified Treatment Phase of the study for an individual patient.

6 STUDY POPULATION SELECTION

6.1 Study Population

A target sample size of 20 patients (ambulant and non-ambulant boys, ≥ 8 years of age; a minimum of 8 ambulant patients will be enrolled) with DMD who meet the eligibility criteria below will be enrolled.

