2.2 Disease and Treatment

2.2.1 Duchenne Muscular Dystrophy – Epidemiology and Genetic/Biochemical Basis

DMD is a disorder of progressive weakness leading to severe disability and ultimately death caused by a deficiency of the dystrophin protein. The reported prevalence of DMD is 15.9 cases per 100,000 live male births in the US and 19.5 cases per 100,000 live male births in the United Kingdom (Ryder et al, 2017; Mendell et al, 2012; Moat et al, 2013). The symptoms of DMD are often first noted at about 3 to 5 years of age, although clinical manifestations may be present as early as the first year of life. Proximal leg weakness impairs mobility and precludes the ability to run or to rise from a squatting position. Complete loss of ambulation follows, with a progressive decline of upper extremity strength and function. Declines in respiratory and cardiac function contribute to morbidity later in the disease, ultimately culminating in early lethality (Birnkrant et al, [Part 1], 2018; Birnkrant et al, [Part 2], 2018). The impact of this debilitating condition on those affected by it and their families is significant.

The biochemical basis of DMD is the absence of a functional dystrophin protein in striated muscle tissue that is essential for healthy muscle function and muscle fiber integrity. In normal striated muscle the cytoplasmic dystrophin protein links intracellular actin with the extracellular matrix to provide structural stability of the muscle cell membrane. In the majority of patients with DMD, dystrophin protein is not produced because of out-of-frame mutations characterized by a deletion of one or more exons from the dystrophin gene, which is located on the short arm of the X chromosome. Dystrophin mutations in which some dystrophin protein function remains are associated with a similar but often milder phenotype, classified as Becker muscular dystrophy (BMD). DMD and BMD exhibit X-linked recessive inheritance.

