12.2 Determination of Sample Size

Assuming a sample size of 20, at least 1 adverse drug reaction with an incidence of 15% may be detected at a probability of $\geq 95\%$ for the safety profile, which is the primary outcome. Based on this, it was decided that 20 patients should be enrolled to confirm safety. A minimum of 8 ambulant patients will be enrolled.

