12.6 Efficacy Assessments

12.6.1 Secondary Objective

The secondary objective is to compare the efficacy of viltolarsen administered IV at weekly doses of 80 mg/kg over a 48-week Treatment Period versus natural history controls in ambulant and non-ambulant boys ≥ 8 years of age with DMD for the following endpoints: absolute and percent predicted PEF, FVC, and FEV1, Brooke and Vignos functional scales, and the NSAA. The PUL and hand-held dynamometry will be described and the change over time estimated for the viltolarsen-treated group only.

In addition to the comparison methods described below, all outcomes for both the viltolarsen-treated and historical control groups will be summarized and tabulated at each time point assessed. Time points in the historical control will match those of the viltolarsen-treated group within pre-defined tolerances. Outcomes at baseline will be compared between viltolarsen and control groups using methods appropriate for the distribution of each outcome.

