12.6.1.1 Peak Expiratory Flow

The change in both absolute and percent predicted PEF rate over the length of the study will be compared between patients receiving viltolarsen and the historical control group using mixed models with repeated measures. These models allow the use of all available assessments per patient, will include a random term per individual, and will assess the additional predictive value of a random slope term. Covariates of age and baseline value will be included. Steroid exposure

will be evaluated and included as an additional covariate if necessary. The pulmonary outcome will be the dependent variable, time and treatment group will be the independent variables, and a time by treatment group interaction will be included if appropriate. Percent predicted values will be calculated from absolute values using equations based on age, height, and ethnicity (see SRM for details).

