12.6.1.4 Brooke and Vignos Scales

Brooke scale: The change in the Brooke function scale over the length of the study will be compared between patients receiving viltolarsen and the historical control group using mixed models with repeated measures. These models allow the use of all available assessments per patient, will include a random term per individual, and will assess the additional predictive value of a random slope term. These models also have the flexibility to adequately model the quasi-continuous nature of the Brooke functional scale. The pulmonary outcome will be the dependent variable, time and treatment group will be the independent variables, and a time by treatment group interaction will be included if appropriate. Covariates of age and baseline value will be included and steroid exposure will be evaluated and included as an additional covariate if necessary.

Vignos scale: The change in the Vignos functional scale will use the same methods described above for the Brooke functional scale.

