12.6.1.8 Analyses Comparing NS-065/NCNP-01 Patients to Historical Controls

A matched data set from the CINRG DNHS data will be created. The purpose of the matching is to create a group data set that corresponds in characteristics to the patients in this study. The CINRG DNHS data set includes patients from 2 years old to over 30 years old, some of whom have been followed for close to a decade. Therefore, it is important to create a comparator group which will allow valid group comparisons. No patient-to-patient matched analysis is proposed. The sole purpose of the matching is to create a historical control group which is comparable in its basic characteristics to the study patient group. The final CINRG DNHS data set is expected to have between 16 and 32 patients included with time intervals of evaluations between 6 and 15 months.

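### The comparison with natural history controls pools ambulant and non-ambulant boys, but ambulatory status is neither a named matching variable nor a covariate for PEF, FVC, FEV1 and Brooke

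*Combined protocol and SAP*

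**What the plan says.** Both main objectives cover the two stages together. Section 3 states the primary objective "in ambulant and non-ambulant boys", and section 12.6.1 states the comparison "versus natural history controls in ambulant and non-ambulant boys". The only rule on composition is in section 6.1: "a minimum of 8 ambulant patients will be enrolled" out of a target of 20.

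For the comparison itself:

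- **Pulmonary endpoints.** Section 12.6.1.1 (PEF) says "Covariates of age and baseline value will be included", with steroid exposure added if necessary. Sections 12.6.1.2 and 12.6.1.3 apply the same model to FVC and FEV1.
- **Brooke and Vignos.** Section 12.6.1.4: "Covariates of age and baseline value will be included and steroid exposure will be evaluated and included as an additional covariate if necessary".
- **NSAA.** Section 12.6.1.7 uses the same covariates and does not restrict the comparison to ambulant boys.
- **Controls.** Section 12.6.1.8 builds a group-level match from the CINRG DNHS that should be "comparable in its basic characteristics to the study patient group". It does not list those characteristics.

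Section 2.2.1 describes a staged disease. Leg weakness comes first, then "Complete loss of ambulation follows, with a progressive decline of upper extremity strength and function", with respiratory and cardiac decline later. Section 9.16.1.3 supplies a ready definition of status: Vignos 1 to 6 is ambulant and 7 to 10 is non-ambulant.

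**The concern.** This is a non-randomised comparison of 20 treated boys with 16 to 32 historical controls, so matching and model adjustment are the only protection against a difference in prognosis. By the protocol's own description, expected one-year change in pulmonary function or upper-limb grade depends on where a boy stands in the sequence. Loss of ambulation is the clearest marker of that position recorded in both groups.

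Age and baseline value are proxies for stage. Two boys of the same age and the same FVC can be on either side of loss of ambulation. If the treated group has more ambulant boys than the controls, and non-ambulant boys lose pulmonary function faster, the untreated difference in decline favours viltolarsen. With the imbalance reversed, it counts against the drug. The enrolment rule allows 8 to 20 ambulant boys, so the treated share can be anywhere from 40% to 100%. Nothing written obliges the control set to follow it.

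**Working it through.** **The plan's own figure.** Section 12.2 justifies 20 patients by safety alone: "Assuming a sample size of 20, at least 1 adverse drug reaction with an incidence of 15% may be detected" with probability of at least 95%. The check is 1 − 0.85^20 = 0.961, so the figure holds. It is a pooled figure. For the split 8 ambulant and 12 non-ambulant, the same formula gives 1 − 0.85^8 = 0.728 and 1 − 0.85^12 = 0.858. No power or precision is stated for the comparison with controls.

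**Bias before adjustment.** Bias = (difference in ambulant share) × (difference in mean change between stages). The documents give neither quantity. Assume that non-ambulant boys lose 3 to 5 more percent-predicted points per year:

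- 60% versus 40% ambulant: 0.20 × 3 = 0.6 to 0.20 × 5 = 1.0 points
- 80% versus 40%: 0.40 × 3 = 1.2 to 0.40 × 5 = 2.0 points
- 100% versus 50%: 0.50 × 3 = 1.5 to 0.50 × 5 = 2.5 points

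**Bias after the planned adjustment.** This comes from a simulation with no drug effect: 20 treated, 24 controls, SD of change 7 (assumed), and least squares of 12-month change on group, age and baseline value, with 3,000 trials per scenario. The last column divides the bias by the standard error (SE) of the group effect, which is 2.2 at modest imbalance and 2.4 at the extreme. The 80/40 row takes 2.2.

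| Ambulant share, treated vs control | Spurious effect, points (3 / 5 per year) | In SEs |
|---|---|---|
| 60% vs 40% | 0.25 / 0.48 | 0.11 / 0.22 |
| 80% vs 40% | 0.62 / 1.01 | 0.28 / 0.46 |
| 100% vs 50% | 0.87 / 1.42 | 0.36 / 0.59 |

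Age and baseline value therefore remove about half of the crude bias: what survives runs from 0.25/0.6 = 42% to 0.87/1.5 = 58%. With ambulatory status added, every value falls to within 0.04 of zero. The SE stays at about 2.2 at modest imbalance and rises from 2.4 to 2.7 at the extreme.

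**Sensitivity.** The surviving part depends on how strongly age and baseline value track status. With ambulant boys assumed 4 years younger and 15 points higher at baseline, the same three rows are 0.33/0.48, 0.62/1.02 and 1.00/1.63. Over other assumed gaps the range is 0.17 to 2.21 points.

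**Effect on error rate.** A shift of d SEs gives a two-sided 5% test a rejection probability of P(Z > 1.96 − d) + P(Z < −1.96 − d). At d = 0.11 this is just above 5%; at d = 0.59 it is 9.1%.

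**Endpoints where status adds little.** For Vignos the baseline value is itself the definition of status. For NSAA, section 9.16.1.5 describes a scale designed for boys who can walk at least 10 metres, with 0 meaning completely non-ambulant. Boys already at 0 cannot decline, so the issue there is who belongs in the comparison rather than which covariate to add.

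**The case against.** The strongest reply is that matching exists to prevent this. Controls are to resemble whoever enrols, so 100% versus 50% ambulant would mean the matching had failed. Section 12.1 also leaves detail to an SAP finalised before database lock, and ambulatory status may appear there. Both points stand. They limit the claim to what is not yet written and make the smaller imbalances the more likely ones. They also make this the time to name the variable, before the control set is drawn.

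The bias is also less than one SE in every row of the table, the decline rates and their direction are assumed, and the simulation uses a single change score instead of the planned repeated-measures model. All of that is correct. Sampling error dominates, and the figures illustrate size without estimating it.

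Three stronger readings are tempting, and the documents do not support them.

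- A reader might infer that the plan promises separate answers for ambulant and non-ambulant boys and fails to deliver them. The objectives name the two groups as one population, and the sample size is pooled. A minimum for non-ambulant boys and safety tables by status would be reasonable preferences, but their absence is not an error.
- A reader might infer that the report could not show how many non-ambulant boys were studied. Section 12.4 summarises baseline efficacy parameters, which include Vignos. Section 12.6.1 tabulates all outcomes in both groups and compares them at baseline, so a marked imbalance in stage would be visible.
- A reader might infer that the comparison is biased. The documents show only that a known route to bias is not closed.

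**Conclusion.** The concern holds in a limited form. For PEF, FVC, FEV1 and Brooke, the written plan neither matches on ambulatory status by name nor adjusts for it, and age and baseline value are only partial substitutes. A difference in ambulant share between treated boys and controls can then pass as a treatment effect. Under an assumed extra loss of 3 to 5 percent-predicted points per year in non-ambulant boys and an SD of change of 7, the size for the pulmonary endpoints is about 0.25 to 1.4 points, or 0.1 to 0.6 SE. Other assumed links between status, age and baseline value widen this to 0.17 to 2.21 points. No corresponding figure was worked out for Brooke, where the argument rests on the staged course in section 2.2.1. The point should be fixed because the remedy is nearly free. It does not by itself undermine the study.

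**What to change.** 1. In 12.6.1.8, name baseline ambulatory status as a matching variable, defined as Vignos 1 to 6 versus 7 to 10 and applied identically at the index visit in both groups.
2. In 12.6.1.1 to 12.6.1.4, add baseline ambulatory status as a covariate in the models for PEF, FVC, FEV1 and Brooke. Where the treatment effect is read from the time-by-treatment term, give status its own interaction with time, because a main effect alone does not adjust a difference in slope. Status can be left out of the Vignos model, where it is largely redundant.
3. In 12.6.1.7, make the NSAA comparison in boys ambulant at baseline in both groups.
4. Optionally, show the efficacy summaries by status. With 8 to 12 boys in a stratum these would be descriptive only.

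No new data are needed. Vignos is part of every function assessment, and the controls must carry it because 12.6.1.4 compares it with them. The cost is one degree of freedom per model (a further one for an interaction with linear time) and a modest loss of precision if imbalance is extreme (SE about 2.4 to 2.7 in the simulation). If all enrolled boys prove to be ambulant, matching on status makes the control set all ambulant too and the covariate drops out.

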6.2 Inclusion Criteria

1. Patient (if age 18 years or older) or patient's parent(s) or legal guardian(s) has (have) provided written informed consent and Health Insurance Portability and Accountability Act (HIPAA) authorization, where applicable, prior to any study-related procedures; patients younger than age 18 years will be asked to give written or verbal assent according to local requirements;
2. Patient has a confirmed diagnosis of DMD defined as:
 - a. Patient is male with clinical signs compatible with DMD; and
 - b. Patient has a confirmed DMD mutation(s) in the dystrophin gene that is amenable to skipping of exon 53 to restore the dystrophin mRNA reading frame including determination of unambiguously defined exon boundaries (using techniques such as multiplex ligation-dependent probe amplification, comparative genomic hybridization array, or other techniques with similar capability);
3. Patient is ≥ 8 years of age at time of first infusion in the study;
4. Patient has a Brooke scale rating of 3 or better OR an upright FVC 30% or greater at Screening;
5. Patient, if sexually active, is willing to abstain from sexual intercourse or employ a barrier or medical method of contraception during and for 3 months following completion of IP administration;
6. Patient and patient's parent(s)/guardian(s) (if patient is < 18 years of age) and/or caregiver(s) are willing and able to comply with scheduled visits, IP administration plan, and study procedures;
7. Patient must be on a stable dose of GC or not treated with GC for at least 3 months prior to the first dose of IP and is expected to remain on the stable dose of GC treatment or off GC for the duration of the study.

